9.8. Sample Handling

Not applicable

9.9. Early Discontinuation/Withdrawal of Participants

During the course of the trial a participant may choose to withdraw their consent, meaning that they wish to withdraw from the study completely. Participants will have the following three options for withdrawal:

- 1) Participants may withdraw from active follow-up and further communication but allow the trial team to continue to access their medical records and any relevant hospital data that is recorded as part of routine standard of care; i.e., scans, blood results and GP records.
- 2) Participants can withdraw from the study but permit data and samples obtained up until the point of withdrawal to be retained for use in the study analysis. No further data would be collected after withdrawal.
- 3) Participants can withdraw completely from the study and withdraw the data and samples collected up until the point of withdrawal. The data and samples already collected would not be used in the final study analysis.

9.10. Definition of End of Trial

The end of trial is the point at which all the 3-year follow up data has been entered and all queries resolved.

10. TRIAL INTERVENTIONS

N/A - observational trial

10.1. Investigational Medicinal Product(s) (IMP) Description

IRAS ID: 301556

N/A

10.1.1. Blinding of IMPs

N/A

10.1.2. Storage of IMP

N/A

10.1.3. Compliance with Trial Treatment

N/A

10.1.4. Accountability of the Trial Treatment

N/A

10.1.5. Concomitant Medication

N/A

10.1.6. Post-trial Treatment

N/A

10.2. Other Treatments (non-IMPS)

N/A

10.3. Other Interventions

N/A

11. SAFETY REPORTING

As this is an observational trial no adverse events are anticipated.

11.1. Adverse Event Definitions

Adverse Event (AE)	Any untoward medical occurrence in a participant to whom a medicine product has been administered, including occurrences which are no necessarily caused by or related to that product.	
Adverse Reaction (AR)	An untoward and unintended response in a participant to an investigational medicinal product which is related to any dose administered to that participant.	
	The phrase "response to an investigational medicinal product" means that a causal relationship between a trial medication and an AE is at least a reasonable possibility, i.e. the relationship cannot be ruled out.	

IRAS ID: 301556

	All cases judged by either the reporting medically qualified professional or the Sponsor as having a reasonable suspected causal relationship to the trial medication qualify as adverse reactions.
Serious Adverse Event (SAE)	 A serious adverse event is any untoward medical occurrence that: results in death is life-threatening requires inpatient hospitalisation or prolongation of existing hospitalisation results in persistent or significant disability/incapacity consists of a congenital anomaly or birth defect*. Other 'important medical events' may also be considered a serious adverse event when, based upon appropriate medical judgement, the event may jeopardise the participant and may require medical or surgical intervention to prevent one of the outcomes listed above. NOTE: The term "life-threatening" in the definition of "serious" refers to an event in which the participant was at risk of death at the time of the event; it does not refer to an event which hypothetically might have caused death if it were more severe.
Serious Adverse Reaction (SAR)	An adverse event that is both serious and, in the opinion of the reporting Investigator, believed with reasonable probability to be due to one of the trial treatments, based on the information provided.
Suspected Unexpected Serious Adverse Reaction (SUSAR)	A serious adverse reaction, the nature and severity of which is not consistent with the Reference Safety Information for the medicinal product in question set out: • in the case of a product with a marketing authorisation, in the approved summary of product characteristics (SmPC) for that product • in the case of any other investigational medicinal product, in the approved investigator's brochure (IB) relating to the trial in question.

NB: to avoid confusion or misunderstanding of the difference between the terms "serious" and "severe", the following note of clarification is provided: "Severe" is often used to describe intensity of a specific event, which may be of relatively minor medical significance. "Seriousness" is the regulatory definition supplied above.

11.2. Assessment results outside of normal parameters as AEs and SAEs

IRAS ID: 301556

N/A

11.3. Assessment of Causality

N/A

11.4. Procedures for Reporting Adverse Events

Adverse events will not be reported as this is an observational trial.

11.5. Reporting Procedures for Serious Adverse Events

Serious adverse events will not be reported as this is an observational trial.

11.5.1. Events exempt from immediate reporting as SAEs

N/A

11.5.2. Procedure for immediate reporting of Serious Adverse Events

N/A

11.6. Expectedness

N/A

11.7. SUSAR Reporting

N/A

11.8. Development Safety Update Reports

N/A

12. STATISTICS

12.1. Statistical Analysis Plan (SAP)

The plan for the statistical analysis of the trial are outlined below. There is not a separate SAP document in use for the trial.

12.2. Description of Statistical Methods

Continuous data will be summarized using descriptive statistics (mean, median, standard deviation, quartiles, minimum and maximum) and categorical data will be summarized using counts and

IRAS ID: 301556

percentages. The proportion of patients undergoing operative compared to non-operative treatment will be reported.

Primary endpoint

The primary endpoint will be reported as the percentage of patients re-admitted with gallstone related problems after operative vs non-operative management during their index admission.

Secondary endpoints

Data will be reported at 30 days, 1 year and 3 years. Patients who have had complications or have died in each group will be reported as a number and percentage. Comparison between groups will be carried out using Chi squared test. Gastrointestinal Quality of Life Index (GIQLI) in each group will be reported as a median and range. Paired T test will be used to compare groups.

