6. OBJECTIVES AND OUTCOME MEASURES

Objectives	Outcome Measures	Timepoint(s) of evaluation of this outcome measure (if applicable)
Primary Objective To compare the rate of gallstone- related hospital re-admission between patients treated operatively and non-operatively	Number and percentage of patients readmitted to hospital with gallstone-related disease by each timepoint.	30 days, 1 year, 3 years
1. To compare morbidity in operative and non-operative groups 2. To compare mortality in operative and non-operative groups 3. To compare quality of life in operative and non-operative groups	Number and percentage of patients with complications in each group Number and percentage of patients who have died in each group Gastrointestinal Quality of Life Index (GIQLI) in each group	30 days, 1 year, 3 years
Exploratory Objectives To assess the result of frailty on		

IRAS ID: 301556

morbidity, mortality and quality of	Morbidity, mortality and quality of life	30 days, 1 year, 3	l
life (as defined above)	according to Rockwood frailty score	years	l
To assess whether frailty affects	Comparison of Rockwood frailty score in		
whether or not surgery is carried	operative and non-operative groups both		
out	before and after surgery.		l
	- ,		

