7. TRIAL DESIGN

This is an observational multicentre cohort study which will take place in a number of hospitals in Wessex. Patients will be recruited to the trial during admission for gallstone disease and followed up for 3 years after this admission. At each follow up timepoint patients will be contacted and asked to complete a quality of life questionnaire and will also be asked whether they have had any further admissions with gallstone related disease. Follow up information may also be obtained from hospital and GP records where appropriate.

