9.7. Subsequent Visits

Patients will be contacted by telephone at 30 days, 1 year and 3 years from registration. Prior to any contact, the hospital EPR and CHiE will be checked to ensure that the patient is still alive.

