12.3. Sample Size Determination

From previous studies, we estimate an approximate readmission rate of at least 30% in patients who do not have surgery compared to 5% in those who do. We estimate that approximately 10% of patients over 70 will not have surgery therefore the enrolment ratio is likely to be 1:9. Using an alpha of 0.05 and a power of 0.9 the number of patients required would therefore be 260. We would aim to recruit a minimum of 290 patients to account for a maximum of 10% lost to follow up.

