12.4. Analysis Populations

All patients as registered. Comparisons will be made between groups who had surgery during/after their index admission and those who were treated non-operatively in assessing the primary endpoint.

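### The primary readmission percentage has no rule for death or incomplete follow-up, so it mixes gallstone recurrence with survival if mortality differs between the groups

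*Protocol*

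**What the plan says.** The primary outcome in Protocol section 6 is "Number and percentage of patients readmitted to hospital with gallstone-related disease by each timepoint", with timepoints at 30 days, 1 year and 3 years. Section 12.2 repeats this as a simple percentage: "The primary endpoint will be reported as the percentage of patients re-admitted with gallstone related problems". Section 12.4 gives the population as "All patients as registered".

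Death appears only as a separate secondary outcome (sections 6 and 12.2). Section 12.8, on missing data, covers data queries and checking back with the site. It gives no rule for deaths or for incomplete follow-up. Section 12.1 states that no separate SAP is in use, so the point is not deferred to another document.

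On collecting the outcome, section 7 has patients asked about further admissions at each contact and adds: "Follow up information may also be obtained from hospital and GP records where appropriate". Section 9.7 says: "Prior to any contact, the hospital EPR and CHiE will be checked to ensure that the patient is still alive". Section 13.2 names medical records as a data source, with patient questioning where needed.

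The two groups are defined in two ways. Section 12.2 refers to management during the index admission, while section 12.4 says: "Comparisons will be made between groups who had surgery during/after their index admission and those who were treated non-operatively".

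**The concern.** Participants are aged 70 or over and are followed for 3 years. The lay summary (section 2) says that patients not offered surgery are usually those who are older, frail or have other illness. Higher mortality in that group is therefore plausible, and the protocol plans to measure it.

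Someone who dies without a readmission can no longer have one. Among all registered patients, that person stays in the denominator as a non-event. If deaths are more frequent without surgery, the non-operative percentage is pulled down more, for a reason unrelated to gallstones. The lay summary says the results should inform joint decisions about surgery, so a reader needs to know whether a low percentage reflects few recurrences or short survival.

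Data collection adds to this. A patient who is readmitted and then dies between two telephone calls cannot be asked. The check made before each call is described only as a check on vital status, and no sentence requires readmission dates to be taken from the record for people who have died.

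**Working it through.** **Inputs from the Protocol (section 12.3).** The assumed rates are: "we estimate an approximate readmission rate of at least 30% in patients who do not have surgery compared to 5% in those who do". The split is: "approximately 10% of patients over 70 will not have surgery therefore the enrolment ratio is likely to be 1:9". Alpha is 0.05, power 0.9, N = 260, raised to 290 for 10% loss. At 1:9, 260 patients are 26 non-operative and 234 operative.

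**The plan's own figure.** With 30% in the small arm and 5% in the large arm, the two-sided pooled formula gives 21 + 189 = 210 (250 with continuity correction), not 260. The same formula returns 260 if the 5% is placed in the small arm. The step 260/0.9 = 289, about 290, is right. This mismatch is a separate matter. Here the baseline is the power of 26:234 with the rates as stated.

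**Power formula** (two-sided 0.05 assumed; sidedness is not stated). With p̄ = 0.1·p1 + 0.9·p2:

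power = Φ{ [ |p1 − p2| − 1.96·√(p̄(1 − p̄)(1/26 + 1/234)) ] / √( p1(1 − p1)/26 + p2(1 − p2)/234 ) }

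For 30% vs 5%: p̄ = 0.075 and power = Φ[(0.25 − 0.1067)/0.0910] = Φ(1.57) = 0.94.

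**Effect of death.** The documents give no mortality, so the 3-year values below are assumptions, shown as a range. Hazards are taken as constant. With p the readmission risk in the absence of death and d the 3-year mortality:

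- h = −ln(1 − p)/3 and m = −ln(1 − d)/3
- percentage readmitted by 3 years = h/(h + m) × [1 − exp(−3(h + m))] = h/(h + m) × [1 − (1 − p)(1 − d)]

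Example, p = 0.30 and d = 0.50: h = 0.1189, m = 0.2310, so 0.3398 × (1 − 0.35) = 0.221.

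*Identical readmission hazards (p = 30% in both groups):*

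| Mortality, non-op/op | Non-operative | Operative | Difference (points) |
|---|---|---|---|
| 20%/5% | 27.1% | 29.3% | −2.2 |
| 30%/10% | 25.5% | 28.6% | −3.1 |
| 40%/10% | 23.8% | 28.6% | −4.7 |
| 50%/10% | 22.1% | 28.6% | −6.5 |

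The true cause-specific hazard ratio is 1 in every row.

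*Planned rates (p = 30% vs 5%), read as risks in the absence of death:*

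| Mortality, non-op/op | Non-operative | Operative | Difference (points) | Power at 26:234 |
|---|---|---|---|---|
| none | 30.0% | 5.0% | 25.0 | 0.94 |
| 20%/5% | 27.1% | 4.9% | 22.2 | 0.91 |
| 30%/10% | 25.5% | 4.7% | 20.8 | 0.89 |
| 40%/10% | 23.8% | 4.7% | 19.1 | 0.86 |
| 50%/10% | 22.1% | 4.7% | 17.3 | 0.81 |

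The cause-specific hazard ratio is ln(0.70)/ln(0.95) = 6.95 in every row, because it does not depend on mortality.

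**The case against.** **The crude percentage is a legitimate quantity.** With complete follow-up, the percentage readmitted with deaths counted as non-events equals the Aalen-Johansen cumulative incidence with death as a competing event. A reader might infer that the percentage is wrong and that a competing-risks estimate would correct it. It would return the same figure. This objection stands. The weakness is that the plan does not declare this quantity, does not secure it when follow-up is incomplete, and offers nothing that separates recurrence from survival.

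**Losses are not said to count as successes.** A reader might infer from the all-registered population that patients lost to follow-up count as not readmitted. No sentence says so. The increase from 260 to 290 suggests they are not analysed. Section 9.9 removes from the analysis those who withdraw their data, and lets others leave contact while their records remain accessible. The handling of loss is unspecified, and no more than that can be said.

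**Readmissions before death are not shown to be missed.** Section 13.2 names medical records first, and section 7 allows hospital and GP records. The sources exist. What is missing is a requirement to search them for patients who have died.

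**The planned rates may already include deaths.** Section 12.3 takes them from previous studies and does not say they are risks in the absence of death. If they are observed proportions, no further power loss applies. The non-operative rate is also given as a minimum.

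**Mortality will be visible.** Deaths are reported by group at the same timepoints, so a careful reader could set the two results side by side. That helps, but two separate percentages do not show how far one has altered the other.

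**Conclusion.** The concern holds as a gap in defining and analysing the primary endpoint. The plan fixes a crude percentage among all registered patients over 3 years, with no rule for death or incomplete follow-up and no SAP to supply one. If mortality is higher in the non-operative group, the comparison combines recurrence with survival.

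The size depends on mortality the protocol does not give. Over the assumed range, equal readmission hazards would show as about 2 to 6.5 points in favour of non-operative management. At the planned rates, read as risks in the absence of death, the gap narrows from 25 to about 22–17 points, and power goes from 0.94 to about 0.91–0.81 against a target of 0.90. The mildest scenario stays above target.

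A reader might go further and infer that the non-operative group will look better than the operative one. The documents do not support that. At the planned rates the gap did not reverse in any scenario tried. An apparent advantage needs equal or nearly equal readmission hazards, contrary to the plan's own assumption, together with unequal mortality.

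**What to change.** **Section 12.2.** Define the primary analysis as time from registration to first gallstone-related readmission, with death as a competing event and censoring at loss to follow-up. Report:

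- cumulative incidence per group at 30 days, 1 year and 3 years as the absolute risk, noting that with complete follow-up it equals the crude percentage;
- a cause-specific hazard ratio as the comparison that separates recurrence from survival;
- readmission or death as a supporting composite.

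**Sections 12.2 and 12.4.** Reconcile the two definitions of the operative group. Either group by treatment during the index admission, as in section 12.2, or treat later surgery as a time-dependent exposure. If patients operated on later count as operative from registration, the time they had to survive before surgery is credited to the operative group, and the hazard ratio carries immortal-time bias.

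**Section 9.7.** Extend the EPR/CHiE check already made at each timepoint, so that readmission and death dates are extracted for every participant who has not withdrawn from record access, including those who have died.

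**Cost.** A little more data entry and a somewhat fuller analysis. No extra patient contact or recruitment is needed. The date collection is best settled early, since dates not captured during follow-up may be harder to recover later.

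### Section 12.2 fixes chi-squared for deaths and complications with no small-count rule, although the 1:9 split gives expected counts below 5 for outcomes rarer than about 19%

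*Protocol*

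**What the plan says.** Protocol section 12.2, under secondary endpoints, sets the reporting times: "Data will be reported at 30 days, 1 year and 3 years". It then says "Patients who have had complications or have died in each group will be reported as a number and percentage", followed by "Comparison between groups will be carried out using Chi squared test". It names no exact test, no continuity correction and no minimum expected count. Section 12.1 states that the analysis plan is contained in section 12 and that no separate SAP document is in use. Section 12.7 sets the significance level at 0.05.

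The group sizes come from section 12.3: "We estimate that approximately 10% of patients over 70 will not have surgery therefore the enrolment ratio is likely to be 1:9". The same section gives the total: "Using an alpha of 0.05 and a power of 0.9 the number of patients required would therefore be 260", raised to 290 for 10% loss to follow-up. The only event rates in the document are those for readmission, 30% against 5%. It gives none for death or complications.

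**The concern.** The Pearson chi-squared p-value is a large-sample approximation, and it weakens when an expected cell count is small. A 1:9 split puts few patients in the non-operative group, so even a modestly uncommon outcome gives a small expected count there. With one or two events in that group, the reported p-value can look far stronger than the data justify. At low event rates the rejections fall almost entirely on the side of excess events without surgery, and operative against non-operative is the comparison that the study exists to make. A mortality p-value of 0.003 resting on a single death could be read as firm evidence. The usual reply, that the SAP will deal with sparse tables, is not available because the protocol says there is none.

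**Working it through.** **The plan's own figure.** The pooled two-proportion formula (two-sided alpha 0.05, power 0.9, no continuity correction), with 30% in the smaller group as stated, gives 21 + 189 = 210. It gives 26 + 234 = 260 only if the smaller group is assigned the 5% rate. The step to 290 is consistent: 260/0.9 = 289. This does not affect the present point. In the stated direction, 26 against 234 has about 94% power for the primary comparison. I take 260 and 1:9 as planned.

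**Group sizes.** 10% of 260 is 26, leaving 234. With all 290 recruited they are 29 and 261.

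**Expected count in the non-operative group.** E = n × pooled event rate. Setting E = 5 and E = 1 gives the rates below which each threshold is crossed:

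| Non-operative n | E below 5 if rate under | E at or below 1 if rate at or under |
|---|---|---|
| 26 | 5/26 = 19% | 1/26 = 3.8% |
| 29 | 5/29 = 17% | 1/29 = 3.4% |
| 78 (30% of 260, the upper share cited in section 5) | 5/78 = 6.4% | 1/78 = 1.3% |

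**Single tables at 26 against 234.** With a and b events in the non-operative and operative groups and m = a + b,

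X² = 260 × [a(234 − b) − b(26 − a)]² / [26 × 234 × m × (260 − m)].

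- 1 against 0: X² = 260 × 234² / (26 × 234 × 1 × 259) = 9.03, so p = 0.0026. Fisher: a single event falls in the non-operative group with probability 26/260 = 0.10. Mid-p is half of that, 0.05.
- 2 against 2: X² = 260 × (464 − 48)² / (26 × 234 × 4 × 256) = 7.22, so p = 0.007. Fisher gives 0.051. Mid-p subtracts half the probability of the observed table, 0.0476/2, which gives 0.027.

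| Events (non-op / op) | Expected non-op | Chi-squared p | Fisher p | Mid-p |
|---|---|---|---|---|
| 1 / 0 | 0.1 | 0.0026 | 0.10 | 0.050 |
| 2 / 2 | 0.4 | 0.007 | 0.051 | 0.027 |
| 2 / 3 | 0.5 | 0.024 | 0.080 | 0.044 |
| 3 / 7 | 1.0 | 0.032 | 0.066 | 0.039 |

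**Size over all tables at 26 against 234, equal true rates.** Each table's binomial probability is summed where chi-squared rejects.

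| True rate | Chi-squared at 0.05 | Chi-squared at 0.01 |
|---|---|---|
| 1% | 0.042 | 0.036 |
| 2% | 0.041 | 0.025 |
| 5% | 0.037 | 0.014 |
| 10% | 0.041 | 0.011 |
| 20% | 0.050 | 0.0095 |

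Fisher's size at 0.05 is about 0.01 to 0.025 for rates of 1% to 5%. At rates up to 5%, essentially all chi-squared rejections are for excess non-operative events. At 10% the split is 0.0366 against 0.0042, and at 20% it is 0.0329 against 0.0170. Results at 29 against 261 are practically the same.

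**The case against.** The strongest reply is that the test fixed in the plan does its job at the level fixed in the plan. A reader might infer from the tables above that chi-squared inflates false positives at 0.05. It does not: averaged over event totals, its size is 0.037 to 0.050, closer to nominal than Fisher's. Given the event total, the rate does reach 10% with 1 event, 8.0% with 5 and 6.6% with 10, but these are peaks of a sawtooth. It is 1.0%, 2.7%, 1.5%, 2.4%, 3.6% and 5.0% at totals of 2, 3, 6, 7, 8 and 9. Of the totals from 1 to 20, chi-squared and Fisher differ on significance only at 1, 4, 5, 10, 15 and 16. Mid-p gives the same verdicts at 0.05 as chi-squared for totals 1 to 16, counting p = 0.05 as significant. All of this stands.

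It also stands that the split alone does not produce expected counts near 1. That needs a pooled rate of about 4% or less, which the protocol does not state. For 3-year deaths or all complications in patients aged 70 and over, rates of 20% or more are possible, and chi-squared is then adequate. Nor does the error always point against non-operative care, as the 20% row shows.

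The protocol does not say whether a continuity correction applies. With Yates' correction, 1 against 0 gives 0.18 and 2 against 2 gives 0.065, so the concern is with the uncorrected test.

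What the reply does not remove is the error in the p-values themselves. They are read as measures of evidence and not only against 0.05, and at nominal 0.01 the size is too high even when averaged over event totals.

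**Conclusion.** The point holds as a minor one, confined to the secondary comparisons of deaths and complications. As written, the plan would attach p-values that are too small to sparse tables: about 38-fold against Fisher for 1 against 0 (0.10/0.0026), about 7-fold for 2 against 2 (0.051/0.007), and 2- to 3-fold for the other two tables shown. The documents do not support the stronger reading that the plan would systematically declare false differences at 0.05.

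The conclusion rests on three assumptions:
- The non-operative group is about 26 to 29 patients. Section 5 cites up to 30% managed non-operatively, which would shrink the problem. Sections 12.2 and 12.4 also differ on whether surgery after the index admission counts as operative, so the split is uncertain.
- Some outcome is uncommon: under about 19% for expected counts below 5, and under about 4% for counts near 1.
- Chi-squared means the uncorrected Pearson test.

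**What to change.** Add to section 12.2: use Fisher's exact test for any two-group comparison of deaths or complications in which an expected count is below 5, and chi-squared otherwise; report the risk difference with a score or exact 95% confidence interval in either case. The interval matters as much as the test, because it shows how little one or two events in about 26 patients can establish.

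The cost is one sentence. Recruitment, data collection and care are unchanged. The statistical price is that Fisher is conservative in the sparse range. Mid-p is a less conservative alternative that also corrects the p-values, but it gives almost the same verdicts at 0.05 as chi-squared. Whichever is chosen should be named before the event counts are known.

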12.7. The Level of Statistical Significance

The level of statistical significance will be set at 0.05.

12.8. Procedure for Accounting for Missing, Unused, and Spurious Data.

IRAS ID: 301556

Any concerns about incomplete or spurious data will be discussed directly with the person responsible for data collection at the site and an attempt to verify the data will be made (e.g. through re-review of medical records).

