13.2. Data Recording and Record Keeping

Data will be collected from medical records and direct patient questioning if necessary (e.g. in assessing frailty, if this information is not already available in the medical record). Quality of life data will be collected via a questionnaire sent to patients at 30 days, 1 year and 3 years. A named Surgical Registrar at each site

IRAS ID: 301556

will be responsible for data collection and CRF completion. Completed CRFs will be sent to the Wessex Research Collaborative and data will be entered onto Microsoft Excel.

The participants will be identified by a unique trial specific number in any database. The name and any other identifying detail will NOT be included in any trial data electronic file. Electronic CRFs will be kept for 5 years after recruitment has ended in case of need for re-review. Any concerns about incomplete or incorrect data will be discussed directly with the person responsible for data collection at the site and an attempt to verify the data will be made (e.g. through re-review of medical records).

All CRFs and data records in the database to be only identifiable by trial number. The list of trial numbers and link to patient details will be stored separately using fully secured computers within the research office of each site and will not be shared with the sponsoring organisation or the Wessex Research Collaborative.

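### GIQLI at 1 and 3 years is compared among living questionnaire responders only; the plan does not say so, and its missing-data rule cannot repair it

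*Protocol*

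**What the plan says.** All references are to the Protocol.

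- **Outcome and timing (12.2).** "Data will be reported at 30 days, 1 year and 3 years". For quality of life, "Gastrointestinal Quality of Life Index (GIQLI) in each group will be reported as a median and range", followed by "Paired T test will be used to compare groups".
- **Source of the score (13.2).** "Quality of life data will be collected via a questionnaire sent to patients at 30 days, 1 year and 3 years". No proxy or record-based version is described.
- **Contact (9.7).** "Patients will be contacted by telephone at 30 days, 1 year and 3 years from registration". Before each contact "the hospital EPR and CHiE will be checked to ensure that the patient is still alive".
- **Withdrawal (9.9).** The first option ends communication with the patient but keeps access to the medical records.
- **Missing data (12.8).** Concerns about incomplete data go to the person collecting data at the site, and "an attempt to verify the data will be made (e.g. through re-review of medical records"). Section 13.2 repeats this.
- **Loss to follow-up (12.3).** The sample is raised from 260 to 290 "to account for a maximum of 10% lost to follow up".
- **Population (12.4).** All registered patients.
- **Where the analysis plan sits (12.1).** In section 12 itself; no separate SAP is in use.

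**The concern.** The patients are 70 or older and are followed for 3 years, so some will die, some will stop answering, and some will withdraw from contact. For each of them the later GIQLI score is absent. Record review can recover a readmission or a death, but not the patient's own answers. Nothing in 12.2 or 12.8 says what the quality-of-life comparison then means or how absent scores are treated.

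Followed as written, the analysis uses whoever is alive and replies, while 12.4 tells the reader that everyone registered is included. The Lay Summary says that patients not offered surgery are usually elderly, frail or otherwise unwell. If more of them die or fail to reply, and those lost are the less well, the remaining non-operative patients look healthier than their group was. A true quality-of-life disadvantage of non-operative care could then be understated. Quality of life is in the study title, and the Lay Summary says the results are meant to inform shared decisions about surgery.

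**Working it through.** **1. The plan's own figure.** 260 / (1 − 0.10) = 288.9, so 289, stated as 290. This reproduces. It is an allowance on the readmission sample size and says nothing about questionnaire return. At the 1:9 ratio in 12.3, 260 patients are 26 non-operative and 234 operative.

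**2. Which missing GIQLI scores 12.8 can recover.**

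| Reason for no score | Section | Recoverable by site query or record re-review? |
|---|---|---|
| Death | 9.7 | No; no score exists |
| Withdrawal from contact, records kept | 9.9 | No; records hold no GIQLI |
| Alive, questionnaire not returned | 12.3, 13.2 | Not from records; possibly through the scheduled telephone call, but telephone completion is not specified |

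**3. Possible size.** The Protocol gives no mortality, no return rate by group and no GIQLI standard deviation. All inputs in this step are therefore assumptions, apart from the 26 and 234.

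Let GIQLI be normal with SD 20 and the same true mean in both groups. Let survival depend on a normal variable correlated ρ with GIQLI, and let a fraction d of a group die. The survivors' mean then exceeds the group's true mean by

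shift(d) = SD × ρ × φ(z_d) / (1 − d),

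where z_d is the d-quantile of the standard normal and φ its density. The bias (non-operative minus operative) is the difference between the two shifts. With ρ = 0.5, SD × ρ = 10:

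- d = 0.05: 10 × 0.1031 / 0.95 = 1.09
- d = 0.10: 10 × 0.1755 / 0.90 = 1.95
- d = 0.20: 10 × 0.2800 / 0.80 = 3.50
- d = 0.30: 10 × 0.3477 / 0.70 = 4.97
- d = 0.40: 10 × 0.3863 / 0.60 = 6.44

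| Mortality, non-operative vs operative | Bias in points | SE of the difference | Bias / SE | A true 8-point deficit would appear as |
|---|---|---|---|---|
| 20% vs 5% | 3.50 − 1.09 = +2.41 | 4.35 | 0.55 | 8 − 2.41 = 5.6 |
| 30% vs 10% | 4.97 − 1.95 = +3.02 | 4.58 | 0.66 | 8 − 3.02 = 5.0 |
| 40% vs 10% | 6.44 − 1.95 = +4.49 | 4.87 | 0.92 | 8 − 4.49 = 3.5 |
| 20% vs 20% | 0 | 4.37 | 0 | 8.0 |
| 10% vs 30% | 1.95 − 4.97 = −3.02 | 4.24 | −0.71 | 8 + 3.02 = 11.0 |

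The SE uses the survivors among 26 and 234 (for example 26 × 0.80 = 20.8 and 234 × 0.95 = 222.3) and the survivors' variance, 400 × [1 − ρ²λ(λ − z_d)] with λ = φ(z_d)/(1 − d). Simulation of the same set-up agrees with the first three rows to within sampling error.

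The bias scales directly with ρ. Over the first three rows it runs from 2.41 × 0.3/0.5 = 1.4 points at ρ = 0.3 to 4.49 × 0.7/0.5 = 6.3 points at ρ = 0.7. It is zero at ρ = 0. The same formula covers non-return by living patients if that is related to GIQLI in the same way.

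**The case against.** **The direction is not documented.** A reader might infer that the comparison will flatter the non-operative group. The Protocol does not support that: it describes frailty qualitatively and gives no death or return rate for either group. Deaths related to surgery would push the other way. The illustration also starts both groups from equal true GIQLI. If non-operative patients are frailer, the unadjusted comparison already makes them look worse, and survivor selection would offset part of that. The net direction of the raw difference is unknown. This objection stands, and the wording has to be that the comparison may favour that group.

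**Part of the problem is already visible.** Section 12.2 reports deaths by group at the same timepoints, each timepoint has a telephone contact, and record review in 12.8 is only an example. This stands in part. Differential death can be seen but is not linked to GIQLI, and no telephone or proxy completion of the questionnaire is provided for.

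**The loss allowance is not a measure of the harm.** A reader might set the whole 10% allowance against the small non-operative group. It is spread over both groups; at 1:9 it removes about 3 of 29 non-operative patients.

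**Ranking deaths lowest is not a clear remedy.** A reader might infer that it recovers power for quality of life. Much of the apparent gain would be the mortality difference itself. In a non-randomised, unadjusted comparison it carries frailty-driven mortality into the quality-of-life result. If the grouping in 12.4, written for the primary endpoint, were also used here, a patient who died waiting for surgery would become a lowest-ranked non-operative result.

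**The shift is below one standard error on a secondary outcome** at the central assumptions (ρ = 0.5). That is true and limits the severity, but a systematic shift does not diminish as the sample grows.

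**Conclusion.** The point holds. At 1 and 3 years GIQLI is a complete-case comparison of living responders. The stated population does not disclose this, the missing-data rule cannot change it, and 12.1 rules out a later SAP as the place to settle it. This much follows from the text alone.

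The bias is conditional. It may favour the non-operative group by about 2 to 4.5 points if SD is 20, the correlation between GIQLI and survival is 0.5, and 3-year mortality is 20-40% against 5-10%. It is nil if losses are equal or unrelated to GIQLI, and it reverses if the operative group loses more. None of these inputs comes from the Protocol. The change is worth making, but the primary endpoint is unaffected.

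**What to change.** **In 12.2:**

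- Define the GIQLI comparison at each timepoint as conditional on being alive then.
- Beside each result, show per group the numbers dead, alive without GIQLI, and with GIQLI.
- Replace the paired t test with a repeated-measures model for independent groups over 30 days, 1 year and 3 years, with baseline Rockwood score as a covariate, so that living non-responders contribute their earlier scores. To match the definition, take each timepoint's estimate from patients alive at that timepoint; one mixed model over everyone registered would implicitly project scores past death.

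**In 12.8:** state that record re-review does not apply to GIQLI.

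A comparison that ranks deaths lowest is at most an optional sensitivity analysis, labelled as mixing mortality with quality of life.

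**Cost.** Wording in two sections and slightly more analysis, with no new data: vital status, GIQLI and frailty are already collected. The model assumes that scores of living non-responders are missing at random given earlier scores and frailty. Section 9.6 lists no GIQLI at baseline, so a patient without a 30-day score brings no earlier GIQLI value to the 1-year estimate, only the Rockwood score.
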